#### **B.5.3. Delegation of Responsibility**

When specific tasks are delegated by an investigator, including but not limited to conducting the informed consent process, the investigator is responsible for providing appropriate training and adequate supervision of those to whom tasks are delegated. The investigator is accountable for regulatory violations resulting from failure to adequately supervise the conduct of the clinical study.

#### **B.6. Institutional Review Board/Ethics Committee**

Prior to gaining Approval-to-Enroll status, the investigational center will provide to the sponsor documentation verifying that their IRB is registered or that registration has been submitted to the appropriate agency, as applicable according to national/regulatory requirements.

A copy of the written IRB/EC and/or competent authority approval of the protocol (or permission to conduct the study) and Informed Consent Form, must be received by the sponsor before recruitment of patients into the study and shipment of investigational product/equipment. Prior approval must also be obtained for other materials related to patient recruitment or which will be provided to the patient.

Annual IRB/EC approval and renewals will be obtained throughout the duration of the study as required by local/country or IRB/EC requirements. Copies of the Investigator's reports and the IRB/EC continuance of approval must be provided to the sponsor.

## **B.7. Monitoring**

Monitoring will be performed during the study to assess continued compliance with the protocol and applicable regulations. In addition, the monitor verifies that study records are adequately maintained, that data are reported in a satisfactory manner with respect to timeliness, adequacy, and accuracy, and that the Investigator continues to have sufficient staff and facilities to conduct the study safely and effectively. The Investigator/institution guarantees direct access to original source documents by BSC personnel, their designees, and appropriate regulatory authorities.

The study may also be subject to a quality assurance audit by BSC or its designees, as well as inspection by appropriate regulatory authorities. It is important that the Investigator and relevant study personnel are available during on-site monitoring visits or audits and that sufficient time is devoted to the process.

## **B.8. Insurance**

Where required by local/country regulation, proof, and type of insurance coverage, by BSC for patients in the study will be obtained.

## **B.9. Informed Consent**

Patient participation in this clinical study is voluntary. Informed Consent is required from all patients or their legally authorized representative. The Investigator is responsible for ensuring that Informed Consent is obtained prior to the use of any investigational devices, study-required procedures and/or testing, or data collection.

The obtaining and documentation of Informed Consent must be in accordance with the principles of the Declaration of Helsinki, ISO 14155, any applicable national regulations, and local Ethics Committee and/or Regulatory authority body, as applicable. The ICF must be approved by the center's IRB/EC, or central IRB, if applicable.

Boston Scientific will provide a study-specific template of the ICF to investigators participating in this study. The ICF template may be modified to meet the requirements of the investigative center's IRB/EC. Any modification requires approval from BSC prior to use of the form. The ICF must be in a language understandable to the patient and if needed, BSC will assist the center in obtaining a written consent translation. Translated consent forms

must also have IRB/EC approval prior to their use. Privacy language shall be included in the body of the form or as a separate form as applicable.

The process of obtaining Informed Consent shall:

- be conducted by the Principal Investigator or designee authorized to conduct the process,
- include a description of all aspects of the clinical study that are relevant to the patient's decision to participate throughout the clinical study,
- avoid any coercion of or undue influence of patients to participate,
- not waive or appear to waive patient's legal rights,
- use native language that is non-technical and understandable to the patient or his/her legal representative,
- provide ample time for the patient to consider participation and ask questions if necessary,
- ensure important new information is provided to new and existing patients throughout the clinical study.

The ICF shall always be signed and personally dated by the patient or legal representative and by the investigator or an authorized designee responsible for conducting the informed consent process. If a legal representative signs, the patient shall be asked to provide informed consent for continued participation as soon as his/her medical condition allows. The original signed ICF will be retained by the center and a copy of the signed and dated document and any other written information must be given to the person signing the form.

Failure to obtain patient consent will be reported by BSC to the applicable regulatory body according to their requirements (e.g., FDA requirement is within 5 working days of learning of such an event). Any violations of the informed consent process must be reported as deviations to the sponsor and local regulatory authorities (e.g. IRB/EC), as appropriate.

If new information becomes available that can significantly affect a patient's future health and medical care, that information shall be provided to the affected patient(s) in written form via a revised ICF or, in some situations, enrolled patients may be requested to sign and date an addendum to the ICF. In addition to new significant information during the course of a study, other situations may necessitate revision of the ICF, such as if there are amendments to the protocol, a change in Principal Investigator, administrative changes, or following annual review by the IRB/EC. The new version of the ICF must be approved by the IRB/EC. Boston Scientific approval is required if changes to the revised ICF are requested by the center's IRB/EC. The IRB/EC will determine the patient population to be re-consented.

## B.10. Publication Policy

In accordance with the Corporate Policy on the Conduct of Human Subject Research, BSC requires disclosure of its involvement as a sponsor or financial supporter in any publication or presentation relating to a BSC study or its results. In accordance with the Corporate Policy for the Conduct of Human Subject Research, BSC will submit study results for publication (regardless of study outcome) following the conclusion or termination of the study. Boston Scientific Corporation adheres to the Contributorship Criteria set forth in the Uniform Requirements of the International Committee of Medical Journal Editors (ICMJE; <http://www.icmje.org>). In order to ensure the public disclosure of study results in a timely manner, while maintaining an unbiased presentation of study outcomes, BSC personnel may assist authors and investigators in publication preparation provided the following guidelines are followed.

- All authorship and contributorship requirements as described above must be followed.
- BSC involvement in the publication preparation and the BSC Publication Policy should be discussed with the Coordinating Principal Investigator(s) and/or Executive/Steering Committee at the onset of the project.
- The First and Senior authors are the primary drivers of decisions regarding publication content, review, approval, and submission.

## **B.11. Definitions of complication criteria (per van der Gaag article):**

### **Specific PBD (ERCP, PTC) related:**

- **Acute pancreatitis:** Abdominal pain and a serum concentration of pancreatic enzymes (amylase or lipase) three or more times the upper limit of normal, that required more than one night of hospitalization
- **Acute cholecystitis:** No suggestive clinical or radiographic signs of acute cholecystitis before the procedure and if emergency cholecystectomy is subsequently required
- **Perforation:** Retroperitoneal or bowel-wall perforation documented by any radiographic technique or direct visual evidence
- **Stent Occlusion:** Recurring obstructive jaundice with necessary stent replacement

### **Specific surgery related:**

- **Pancreaticojunostomy leakage:** Drain output of any measurable volume of fluid on or after postoperative day 3 with an amylase content greater than 3 times the serum amylase activity, graded according to clinical course (ISGUPS grade A, B, C), or direct visual evidence of defect at anastomosis
- **Delayed gastric emptying:** Gastric stasis requiring nasogastric intubation for 10 days or more, or the inability to tolerate a regular (solid) diet on or before the fourteenth

postoperative day, not due to sequelae of intra-abdominal complications (i.e. abscess, anastomotic leakage)

- **Biliary leakage:** Bilirubin in abdominal drain or dehiscence found at laparotomy
- **Gastro-/duodenojejunostomy leakage:** Conclusive radiographic or direct visual evidence of a defect of the anastomosis
- **Intra-abdominal abscess formation:** Intra-abdominal fluid collection with positive cultures identified by ultrasonography or computed tomography, associated with persistent fever and elevations of white blood cells
- **Wound infection:** Requiring intervention otherwise considered as minor complication
- **Portal Vein Thrombosis:** Conclusive radiologic evidence of thrombosis

**Following either procedure:**

- **Cholangitis:** Elevation in temperature more than 38°C, thought to have a biliary cause, without concomitant evidence of acute cholecystitis, requiring intervention
- **Hemorrhage:** Bleeding after the index procedure requiring transfusion of  $\geq 4$  units of packed cells within a 24-hour period, or leading to relaparotomy/intervention
- **(Emergency) (re)laparotomy:** Any (other) reason following either preoperative biliary drainage or another surgical procedure
- **Pneumonia:** Pulmonary infection with radiological confirmation and requiring antibiotic treatment
- **Mortality:** In-hospital death, due to protocol complications or any cause, including progression of disease, within the study period

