### 3.1. Scale and Duration

Patients that have gone to surgery will be followed for 30 days post-surgery. For patients that have transitioned to palliation, the Long Term Follow-Up Visit will occur one (1) year after initial treatment. Patients that have not gone to surgery and have not transitioned to palliation (with or without Neoadjuvant Therapy) will be followed up to 1 year post-stent placement. There will be 6-12 participating centers with anticipated enrollment of 122 patients.

At each investigational center, there will be one principal investigator (PI) who will be an endoscopist. Where possible at least one co-investigator should be a pancreaticobiliary surgeon.

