### 4.2. Secondary Endpoints

1. Occurrence and severity of adverse events related to the stent and/or stenting procedure
2. Occurrence and severity of surgical complications
3. Occurrence and severity of peri-surgical complications (up to 30 days after surgery)
4. Ability to deploy the stent in satisfactory position across the stricture (Stent Placement Success)
5. Improvement of biliary obstructive symptoms during stent indwell at Week 1 and Monthly until surgery or transition to palliation as applicable, compared to Baseline
6. Improvement of Laboratory Liver Function Tests (LFTs) until surgery for patients undergoing surgery, and at Week 1 and Monthly until transition to palliation, and at 1 year after stent placement for patients not undergoing surgery
7. Biliary Reintervention rate
8. Ability to complete neoadjuvant therapy as intended without stent related interruptions of neoadjuvant therapy
9. Stent migration rate
10. Assessment by surgeon of interference, if any, of SEMS on time to surgery and/or success of pancreaticoduodenectomy
11. For patients transitioning to palliative management: Successful biliary drainage defined as absence of reinterventions for the management of biliary obstructive symptoms from stent placement to 1 year after stent placement

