### 7.13. *Study Completion*

End of study will be reached at:

- Up to 30 days post-surgery for those patients undergoing potential curative intent surgery
- 1 year post stent placement for patients that have transitioned to palliation within 12 months after stent placement
- 1 year post stent placement for patients who do not undergo potential curative intent surgery and do not transition to palliation within 12 months after stent placement (with or without Neoadjuvant Therapy)

End of study will be reached at study completion, at patient withdrawal from study, or at death, whichever comes first.

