**Table 4: Adverse Event Definitions**

Term	Definition
	applicable, see MEDDEV 2.7/3 12/2010 for reporting timeline requirements.
Unanticipated Adverse Device Effect (UADE)  Ref: 21 CFR Part 812	Any serious adverse effect on health or safety or any life-threatening problem or death caused by, or associated with, a device, if that effect, problem, or death was not previously identified in nature, severity, or degree of incidence in the investigational plan or application (including a supplementary plan or application), or any other unanticipated serious problem associated with a device that relates to the rights, safety, or welfare of subjects.
Unanticipated Serious Adverse Device Effect (USADE)  Ref: ISO 14155-2011	Serious adverse device effect which by its nature, incidence, severity, or outcome has not been identified in the current version of the risk analysis report.  Note: Anticipated serious adverse device effect (ASADE) is an effect which by its nature, incidence, severity or outcome has been identified in the risk analysis report.
Device Deficiency  Ref: ISO 14155-2011  Ref: MEDDEV 2.7/3 12/2010	A device deficiency is any inadequacy of a medical device with respect to its identity, quality, durability, reliability, safety or performance.  Note: Device deficiencies include malfunctions, misuse or use errors, and inadequate labeling.  Note: All device deficiencies that could have led to a SADE if suitable action had not been taken or if circumstances had been less fortunate shall be reported as required by the local IRB/EC, national regulations, or the protocol. If applicable, see MEDDEV 2.7/3 12/2010 for reporting timeline requirements.

Abbreviations: EC=Ethics Committee; IRB=Institutional Review Board

Underlying diseases are not reported as AEs unless there is an increase in severity or frequency during the course of the investigation. Death should not be recorded as an AE, but should only be reflected as an outcome of a specific SAE (see **Table 4** for AE definitions).

All device-related events and all surgery related events experienced by the study patient after informed consent, whether during or subsequent to the procedure, must be recorded in the eCRF.

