### **10.2. Relationship to Study Device(s)**

The Investigator must assess the relationship of the AE to the study device as related or unrelated. Unrelated AEs will not be reported. Per protocol, only complications related to stent and/or stenting procedures will be reported. See criteria in **Table 5**.

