### **10.3. *Investigator Reporting Requirements***

Investigators will be required to report all SAEs and ADEs.

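### The only Mortality definition counts in-hospital deaths, so deaths at home within follow-up are not counted under Mortality, and those judged unrelated or due to progression may not be tabulated at all

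*Protocol*

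**What the plan says.** Protocol B.11, under the heading for complications that follow either procedure, defines Mortality as "In-hospital death, due to protocol complications or any cause, including progression of disease, within the study period". SAP 7.3 repeats the definition word for word. Both attribute the criteria to a published article on preoperative biliary drainage. Protocol 9.2 lists mortality among the anticipated surgical adverse events.

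The observation windows are set elsewhere:
- Secondary endpoint 3 (Protocol 4.2, repeated in SAP 5.1) reads "Occurrence and severity of peri-surgical complications (up to 30 days after surgery".
- Protocol 3.1 states: "Patients that have gone to surgery will be followed for 30 days post-surgery". Patients who have neither surgery nor a transition to palliation "will be followed up to 1 year post-stent placement". Patients who move to palliation have a one-year visit.
- Protocol 7.13 states: "End of study will be reached at study completion, at patient withdrawal from study, or at death, whichever comes first".

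The safety sections deal with death as follows:
- Protocol 10.1: "Death should not be recorded as an AE, but should only be reflected as an outcome of a specific SAE".
- Protocol 10.3: "Investigators will be required to report all SAEs and ADEs".
- Protocol 10.2: "Unrelated AEs will not be reported. Per protocol, only complications related to stent and/or stenting procedures will be reported". Section 10.3.2 adds that unrelated adverse events are not collected.

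**The concern.** The definition sets no limit on cause and spans the study period, so it reads like an all-cause count. Yet the place of death decides whether the event qualifies. Two patients who die on the same postoperative day from the same cause are classified differently if one had been discharged. The count then depends on length of stay and on where patients with advanced cancer spend their last days, neither of which is a property of the stent.

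At stake is a safety figure that readers will look for in a trial of a device placed before major surgery. A line labelled Mortality is likely to be read as all deaths in follow-up unless the restriction is spelled out and a complete count stands beside it.

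**Working it through.** The plan states no mortality rate, so there is no figure to reproduce. The check sets the definition against the follow-up windows and the safety-reporting rules.

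**Step 1: how much follow-up is outside hospital.** The pre-operative visits (7.7), the 30-day post-operative visit (7.11) and the long-term visit (7.12) are all headed as phone and/or office visits. The Introduction puts neoadjuvant chemoradiation at 2 to 7 months, with a rest and restaging period after it. The plan therefore expects patients to be at home for most of stent indwell and to have been discharged by the 30-day visit.

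**Step 2: trace typical deaths through the rules.** All of these fall within follow-up.

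| Death | Mortality under B.11 / SAP 7.3? | Other route |
|---|---|---|
| Day 20 after surgery, still in hospital, any cause | Yes | Serious adverse event outcome, if reportable |
| Discharged day 8, dies at home day 20, surgery-related | No | Fatal outcome of a serious adverse event (10.1, 10.3) |
| Same, but judged unrelated to stent and surgery | No | Unclear: 10.3 asks for all serious events, while 10.2 and 10.3.2 exclude unrelated events |
| At home during neoadjuvant therapy, stent-related | No | Fatal outcome of a serious adverse device effect (10.1, 10.3) |
| At home during neoadjuvant therapy, from progression | No | Unclear, as above; 9.1 also leaves normal disease progression out of anticipated device-effect deaths |
| In hospital during neoadjuvant therapy, from progression | Yes | As above |

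The third and fifth rows are the gap. Section 10.1 allows death to appear only as the outcome of a specific serious adverse event. If the underlying event is unrelated and therefore not reported, the death has nothing to attach to. The last row shows that the same progression death in hospital would count.

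**Step 3: look for another planned count.** None of the 11 secondary endpoints is all-cause or 30-day mortality. Under 7.13 any death ends participation, so the fact of death should be known at study exit, but neither document plans to tabulate it by arm. The last-follow-up rule in SAP 7.3 lists seven kinds of date, and date of death is not among them.

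**Step 4: what can be said about size.** The number of misclassified deaths would need a death rate and a distribution of discharge times, and the documents give neither. Only the weight of a single death can be shown, on assumptions about how many patients reach surgery. Take 122 / 2 = 61 per arm with no loss.
- If 25% to 41% do not have the planned resection (Introduction): 61 × 0.75 = 46 and 61 × 0.59 = 36 resected per arm. One death is 1/46 = 2.2 to 1/36 = 2.8 percentage points of a 30-day proportion.
- If 32 of 84 (38%) are resected, as the Introduction reports for borderline resectable disease: 61 × 32/84 = 23 per arm. One death is 1/23 = 4.3 points.

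These figures show how coarse the denominators are. They are not an estimate of bias.

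**Step 5: effect on the primary analysis.** Success is absence of reintervention for biliary obstructive symptoms. The Mortality definition enters neither that endpoint nor the calculation behind 51 per arm, so changing it alters neither.

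**The case against.** The strongest reply is that the deaths are not lost. Leading to death is the first criterion for a serious adverse event in Protocol Table 4 and SAP 7.3, with no limit on place. Section 10.3.1 requires such events within 2 business days, and 10.1 requires all device-related and surgery-related events after consent to be recorded. The complication behind a surgical death would still count under endpoints 2 and 3. The definition is openly labelled in-hospital and comes from a published complication set, which it is legitimate to keep intact. It applies equally to both arms.

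Most of this stands, and it rules out three stronger readings that a reader might infer:
- That no part of the safety data would capture a death after discharge. The serious adverse event route contradicts this for device- and surgery-related deaths.
- That a planned 30-day or pre-operative mortality rate would be too low. No such rate is specified as an endpoint.
- That the comparison between arms would be biased. Nothing in the documents shows that discharge timing or place of death differs by arm.

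The reply does not close the gap in the third and fifth rows of the table. The published source explains the wording but does not fit it to this trial's 30-day and one-year windows. An exit record is patient disposition, not a planned safety analysis.

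**Conclusion.** The concern holds as a narrow mismatch between a definition and the follow-up it serves. Followed as written, the plan makes the Mortality count depend on place of death and may leave some out-of-hospital deaths untabulated. This rests on two assumptions: that the B.11 list governs how complications are reported under the secondary endpoints, since no other mortality definition exists, and that the restriction on unrelated events in 10.2 and 10.3.2 is applied despite the broader wording of 10.3. If all serious events are collected regardless of relationship, the deaths are in the database, and what remains is a matter of labelling and tabulation.

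The size is unknown and cannot be derived from the documents. The consequence is confined to safety and secondary-endpoint reporting. It should be corrected, but it does not threaten the trial's main conclusion.

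**What to change.** In Protocol B.11 and SAP 7.3, define mortality as death from any cause at any location. Tabulate it by arm over two windows: within 30 days of surgery, and from stent placement to study exit. Keep in-hospital death as a separate subset line so that comparison with the published definition remains possible. Confirm that the study-exit record holds the date and place of death.

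The cost is a wording change and one extra table, with no added visits or patients. The mortality figure may look less favourable than the in-hospital count alone. The change should be made before the analysis, because a definition chosen once the deaths are known would look data-driven.
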